The effect of monotherapy with enzalutamide and apalutamide in patients with hormone-naïve prostate cancer has been explored and reported. A single arm phase 2 study by Tombal et al evaluating enzalutamide monotherapy in men with biochemically recurrent and hormonesensitive metastatic prostate cancer showed similar PSA level reduction by enzalutamide monotherapy compared to testosterone suppression treatment with luteinizing hormonereleasing hormone (LHRH) analogues. Enzalutamide alone, however, resulted in a mean increase of testosterone levels of 114% at week 25 with frequent side effects of grades 1-2 such as gynecomastia (36%), fatigue (33%), nipple pain (20%), and hot flush (18%) (Tombal et al. 2014). In this enzalutamide study, peak serum testosterone rise plateaued at around 10 to 13 weeks of treatment. At ASCO 2020, (Maluf et al. 2018) presented data of LACOG 0415, a three-arm phase 2 study exploring efficacy of the ADT-free alternatives in a patient population with advanced hormone-sensitive prostate cancer and biochemical recurrence. The apalutamide monotherapy arm demonstrated similar PSA decline level to the other two arms, however, it too resulted in a high mean increase in levels of serum testosterone of 134.3% at week 25 with high incidences of any grade side effects such as gynecomastia (55%), rash (26%), fatigue (21%), pruritus (17%) and breast pain (14%). In this apalutamide study, peak serum testosterone rise plateaued at around 10 to 13 weeks of treatment.

The increased serum testosterone levels are peripherally converted to estrogens (Fagerlund et al. 2015, Scher et al. 1997) and are suspected to be the cause for the specific feminization side effects like gynecomastia and breast tenderness observed in the above mentioned two trials.

The increase in serum testosterone level observed with enzalutamide and apalutamide is thought to result from the ability of these compounds to penetrate the blood-brain-barrier (BBB), resulting in upregulation of luteinizing hormone signaling due to blockage of the androgen receptor in hypothalamus and pituitary gland which increases testosterone production. Unfortunately, it is not fully established whether this negative feedback loop occurs entirely within the central nervous system (CNS) or whether parts of it may be situated outside of the BBB.

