The conduct of the randomized phase is contingent on the results of the lead-in phase unless data from other ongoing studies could provide similar evidence. Participants will receive darolutamide 600 mg bid or enzalutamide 160 mg once daily for a total duration of 52 weeks until unacceptable toxicity, PSA progression, withdrawal of consent, investigator's or patient's decision to stop therapy, Sponsor's decision to terminate the study, or death. Following the 52-week intervention, all participants will be offered to continue the treatment with darolutamide as per investigator decision, including patients randomized to enzalutamide who would switch to treatment with darolutamide.

Page: 19 of 86

Study Intervention Lead-in phase

Study Intervention	Darolutamide
Dosage Level(s)	Darolutamide 600 mg (2 tablets of 300 mg) will be administered twice daily with food, equivalent to a total daily dose of 1200 mg
Route of Administration	Oral (p.o.)
Use	Experimental

Study Interventions Randomized phase

Study Intervention	Darolutamide
Dosage Level(s)	Darolutamide 600 mg (2 tablets of 300 mg) will be administered twice daily with food, equivalent to a total daily dose of 1200 mg
Route of Administration	Oral (p.o.)
Use	Experimental

Study Intervention	Enzalutamide
Dosage Level(s)	Enzalutamide 160 mg will be administered once daily with or without food
Route of Administration	Oral (p.o.)
Use	Experimental

The expected study duration for the lead-in phase is 18 months assuming 20 evaluable participants are enrolled within an enrollment period of 6 months and treated for 12 months (52 weeks). The expected study duration for the randomized phase is 25 months assuming 40 participants are enrolled within an enrollment period of 12 months. For each phase the primary analysis will be at 12 weeks. The final analysis for both phases will be conducted after all subjects have completed the 52 weeks of treatment and will analyze the long-term results of the secondary endpoints.

1.4.1.1 Lead-in phase:

).

During the lead-in phase 25 participants will be assigned in a single cohort to darolutamide to ensure that 20 participants treated with darolutamide for 12 weeks are evaluable for serum testosterone level at week 12. This sample size will help estimate the mean percent change in serum testosterone level from baseline at 12 weeks within at most +/- 25%, assuming a true mean percent increase of less than 45%. This assessment uses a log normal distribution for percent change.

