The conduct of the randomized phase is binding to a condition of obtaining an estimated mean percent increase from baseline in serum testosterone level at 12 weeks of less than 45%, and non-binding to a condition that the incidence of feminizing side effects observed is below that previously reported (CC)

The Sponsor reserves the right to conduct or stop the lead-in phase in case data on testosterone levels from patients treated with darolutamide alone would become available from other ongoing studies.

Page: 20 of 86

1.4.1.2 Randomized phase:

A maximum of 40 participants (20 per arm) will be randomly assigned to study treatment (darolutamide or enzalutamide) such that approximately 34 evaluable participants complete the study. The randomized stage will require a sample size of 20 per group to provide 85% power to test the null hypothesis of no-difference between groups on mean percent change at two-sided 0.05 level. This assessment is based on a mean percent change in serum testosterone from baseline and Standard Deviation for the darolutamide arm of 45% and 65% versus 110% and 75% respectively for enzalutamide. The final sample size and time of testosterone assessments may be modified according to the results of the lead-in phase.

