4.1 Overall Design

This is a two-stage open label phase 2 study with a lead-in single-arm phase and the randomized phase, to assess the impact of ARI darolutamide or enzalutamide as a monotherapy treatment on serum testosterone levels in men with hormone-naïve prostate cancer experiencing biochemical recurrence (BCR) after failure of treatment with curative intent for localized prostate cancer. Secondary endpoints to be evaluated include the impact of ARI monotherapy on energy metabolism and the metabolism of sex hormones as well as PSA response and safety. Exploratory endpoints will evaluate changes in bone metabolism, physical function, and quality of life profiles. The study design is shown in the Figure 4-1.

In the lead-in phase, approximately 25 participants will be treated with darolutamide for 52 weeks. The primary endpoint analysis of the lead-in phase will occur when all participants in the lead-in phase have been on treatment for 12 weeks, unless the participant discontinued due to lost to follow-up, withdrawal, or death. The secondary endpoint analysis of lead-in phase (see Table 3-1) will occur after patients have been treated for 52 weeks.

[figure not shown]
The study team will review the findings form the lead-in phase of the study, to provide input on interpretation of the results from the lead-in phase which will help guide a decision on the conduct or not of the randomized phase as well as potential changes in the study design for the randomized phase by the Sponsor. In any case, the conduct of the randomized phase is conditional on obtaining a mean percent change in serum testosterone from baseline for the darolutamide arm of less than 45%. Additional non-binding thresholds to help with the decision on the conduct of, or changes in the randomized phase, are that the incidence of feminizing side effects observed is below than that previously reported

Depending on the results of the evaluation and in case of the decision to proceed with the randomized phase, the primary endpoint may be modified, and the statistical assumptions revised. The Sponsor withholds the right to conduct or stop the lead-in phase or start the randomized phase in case data on testosterone levels from patients treated with darolutamide alone would become available from other ongoing studies.

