8.8 Physical Examinations

A complete routine physical examination will be conducted at baseline and at EOT visit. Weight will also be measured and recorded.

Investigators should pay special attention to clinical signs related to previous serious illnesses.

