1.2. Study Design

1.2.1 Overall Design

This is a two-stage open-label phase 2 study with a lead-in single-arm phase and the randomized phase, to assess the impact of androgen receptor inhibitor (ARI) darolutamide or enzalutamide as a monotherapy treatment on serum testosterone levels in men with hormone-naïve prostate cancer experiencing BCR. The study design is shown in Figure 1-1.

Figure 1-1: Overall Design

Abbreviations: ECOG Eastern cooperative oncology group, PC prostate cancer, PSADT PSA doubling time.

In the lead-in phase, participants will be treated with darolutamide (600 mg twice daily). The primary analysis of the lead-in phase will occur when the last participant in the lead-in phase has been on treatment for 12 weeks, unless the participant discontinued due to lost to follow-up, withdrawal, or death. Analysis will be based on a date-based data cut in which the cutoff date will be the last participant week 12 visit date.

The study team will review the findings from the lead-in phase and provide input on interpretation of the results from the lead-in phase. This will help guide a decision on go/no-go with the randomized phase as well as potential changes in the study design for the randomized phase by the sponsor.

In case of the decision to proceed in the randomized phase, participants will be randomized in a 1:1 ratio to receive either darolutamide (600 mg twice daily) or enzalutamide (160 mg once daily). The primary analysis of randomized phase will be conducted when the last participant in the randomized phase has been on treatment for at least 12 weeks. Similar to lead-in phase the analysis will be based on a date-based data cut.

The final analysis for both phases of the study will occur when last participant in the randomized phase has been on treatment for at least 52 weeks, unless the participant discontinued due to lost to follow-up, withdrawal, or death.

The overall sample size across the two phases is expected to be about 65 participants.

The study will comprise the following consecutive periods: Screening, Treatment, and Active Follow–up.

ARAMON V3.0 Page: 9 of 31

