All grades of the feminizing side effects of gynecomastia (including breast enlargement, breast mass, breast swelling), breast tenderness/pain, nipple pain, and hot flush will be summarized using frequencies and percentages. Incidence of AEs of special topics (Bone fractures excluding pathological fractures, Cerebral ischemia, Diabetes mellitus and Hyperglycaemia, Fall, Fatigue/ asthenic conditions, Weight decreased, Rash, Seizure, Hypertension, Vasodilatation and flushing, Mental impairment disorders, Depressed mood disorders, Breast disorders/gynecomastia, Cardiac disorders, Cerebral and intracranial hemorrhage) associated with ARI treatment will also be presented.

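### The non-binding lead-in condition on feminizing side effects sets a crude percentage over mixed follow-up against a previously reported rate, so the reading depends partly on enrolment pace

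*Protocol*

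**What the plan says.** Protocol 1.4.1.1 sets two conditions for opening the randomized phase. The binding one is an estimated mean testosterone increase below 45% at week 12. The other is "non-binding to a condition that the incidence of feminizing side effects observed is below that previously reported". Section 4.1 repeats it under "Additional non-binding thresholds to help with the decision on the conduct of, or changes in the randomized phase". The public copy breaks off where the benchmark would be stated, so its value and time window cannot be seen.

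For the lead-in primary analysis, SAP 1.2.1 says: "Analysis will be based on a date-based data cut in which the cutoff date will be the last participant week 12 visit date". SAP 4.1.1 ties PSA response to weeks 4 and 12 but lists treatment-emergent adverse events without a week. SAP 4.5.2 counts an event from first dose to 30 days after last dose, so for men still on treatment, counting runs to the cut. On the summary statistic, SAP 4.3.1.1 says that gynecomastia (with related breast terms), "breast tenderness/pain, nipple pain, and hot flush will be summarized using frequencies and percentages". SAP 4.5.2 adds counts of subjects only. SAP 4.6.1 adds median treatment duration for this analysis.

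Protocol 1.4.1 plans the lead-in "assuming 20 evaluable participants are enrolled within an enrollment period of 6 months and treated for 12 months".

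**The concern.** Feminizing effects can first appear at any point during treatment, so the proportion of men who have had one rises with time on drug. At a calendar cut, the first man enrolled has been observed for 12 weeks plus the whole enrolment period, and the last man for 12 weeks. A crude percentage averages over that spread, and the spread is set by recruitment. Fast recruitment lowers the percentage and slow recruitment raises it, with the drug unchanged.

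The percentage is then compared with a rate from other studies that had their own follow-up. If the durations differ, a result below the reported rate may reflect shorter observation. A result above it may reflect longer observation. Fewer feminizing effects is part of the protocol's case for darolutamide (1.2 and 4.4). The study team and sponsor will read this number when they decide whether to proceed or change the design.

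**Working it through.** **Inputs from the documents.** 25 men are assigned in the lead-in (protocol 9.2.1). Enrolment takes 6 months (1.4.1). The cut is at the last man's week 12 (SAP 1.2.1). Gynecomastia on enzalutamide monotherapy was 36% (protocol 1.2).

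**Assumptions.** The 36% accrued by week 25, the hazard is constant, and entry is uniform over the enrolment period. Protocol 1.2 attaches week 25 to the testosterone increase and gives no window for the adverse-event rates, so the 25-week window is mine. Gynecomastia stands in for the wider group of feminizing effects.

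**The plan's own figure.** 6 months of enrolment + 12 months of treatment = 18 months, which matches the stated lead-in duration.

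**Follow-up at the cut.** The last man has 12 weeks. The first has about 26 + 12 = 38 weeks. Visit windows of ±7 days and early discontinuation blur both ends.

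**Hazard.** λ = −ln(1 − 0.36)/25 = 0.01785 per week. The risk is 1 − exp(−12λ) = 19.3% by week 12 and 1 − exp(−38λ) = 49.3% by week 38.

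**Expected crude incidence.** With an enrolment period of A weeks, follow-up is uniform on 12 to 12 + A, and

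p(A) = 1 − [exp(−12λ) − exp(−(12 + A)λ)]/(Aλ).

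For A = 26: 1 − (0.8072 − 0.5074)/0.4641 = 0.354.

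**Chance of falling below 36%.** Since 9/25 is exactly 36%, the condition needs 8 or fewer events. The probability is binomial, P(X ≤ 8) with n = 25. The table gives it for a drug with the benchmark hazard and for one with half that hazard.

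| Enrolment | Expected crude incidence, same hazard | P(below 36%), same hazard | P(below 36%), half hazard |
|---|---|---|---|
| Immediate | 19.3% | 0.96 | >0.999 |
| 3 months (A = 13) | 28.0% | 0.755 | 0.99 |
| 6 months (A = 26, planned) | 35.4% | 0.45 | 0.96 |
| 12 months (A = 52, not planned for the lead-in) | 47.4% | 0.09 | 0.75 |

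Setting the cut by the simulated last entrant gives 0.96, 0.78 and 0.50 for the first three same-hazard rows.

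**Sensitivity, same hazard, immediate versus 6-month enrolment (simulated).** Early-onset hazard (Weibull shape 0.5): 0.80 versus 0.47. Late-onset (shape 2): above 0.99 versus 0.50. Benchmark 20% at 25 weeks: 0.90 versus 0.47. Benchmark 55% at 25 weeks: 0.99 versus 0.57.

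**If the 36% had accrued over 52 weeks.** λ = −ln(0.64)/52 = 0.00858. Expected incidence is 9.8% and 19.1%, and the chance of falling below 36% is above 0.999 and 0.96. Pace then matters little, but a drug no better than the benchmark almost always meets the condition, because the durations do not match.

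**After the change.** With a week-12 estimate read against a week-12 benchmark (19.3% under the same assumptions), 4 or fewer of 25 are needed. The chance is 0.46 for a drug equal to the benchmark and 0.90 for one with half its hazard, whatever the enrolment pace. A week-12 estimate read against the unmatched 36% would still be met with probability 0.96 by a drug no better, so both windows must be aligned.

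**Men with 24 weeks of follow-up at the cut.** 6-month enrolment: 25 × 14/26, about 13. 3-month: 25 × 1/13, about 2. Immediate: none.

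**The case against.** The strongest reply is that this is an aid to judgement. The condition is non-binding and the study team reviews it with everything else. The binding criterion is testosterone at a fixed week 12, which enrolment pace does not affect. That stands.

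The benchmark is also redacted. Its value, event definition and window may all be stated in the hidden text, and week 25 belongs to the testosterone result. This stands too: the 36%-by-week-25 figures are an illustration, and nothing here treats the redaction as an omission.

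At the planned 6 months, mean follow-up is (12 + 38)/2 = 25 weeks and expected incidence is 35.4% against 36%. Against a 25-week benchmark the distortion is therefore close to nil if recruitment runs to plan. Sampling noise is also large with 25 men.

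Median treatment duration is reported with this analysis, so readers will see the exposure. It does not adjust the percentage or put it on the benchmark's time scale.

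A reader might infer that enrolment pace, not the drug, decides whether the condition is met, or even whether the randomized phase opens. The documents do not support either. The condition cannot decide the second question alone. On the first, a drug with half the benchmark hazard still meets the condition with probability of about 0.96 or more at any pace up to the planned one.

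What remains is that nothing visible in the SAP gives these events a fixed window or adjusts for exposure, whatever the benchmark is.

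**Conclusion.** The concern holds in a limited form. The crude lead-in percentage of feminizing side effects depends partly on enrolment pace, because follow-up at the cut runs from 12 to about 38 weeks under the planned enrolment. Under the illustrative assumptions, a drug no better than the benchmark meets the condition with probability 0.96, 0.755 or 0.45 for immediate, 3-month or 6-month enrolment.

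The effect is small against a 25-week benchmark if enrolment takes 6 months. It matters mainly when the drug's hazard is close to the benchmark, which is where a threshold is supposed to discriminate. The mixed follow-up and the crude summary come straight from the documents. The probabilities rest on the assumed 36%, the 25-week window, the hazard shape and uniform entry. This is a worthwhile and cheap improvement to an advisory comparison. It does not undermine the go/no-go rule.

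**What to change.** In SAP 4.3.1.1 and 4.5.2, for the lead-in primary analysis, add the Kaplan-Meier cumulative incidence of each feminizing side effect, censored at the data cut or 30 days after last dose:

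- at week 12, which every man still on study has reached by the cut;
- at week 24, with number at risk and confidence interval, where enough men have that follow-up.

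In protocol 4.1, state that the non-binding condition is read against the previously reported rate over a matching treatment duration where that duration is known, and is otherwise descriptive. Keep the crude percentage and median treatment duration as description.

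The cost is one extra table from onset dates already collected and one protocol sentence, with no change to visits or sample size. The downside is that the week-24 estimate will be imprecise, or not estimable, if enrolment is fast. The week-12 estimate helps the comparison only where a reported rate over a similar duration exists.

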1.4.1.3 Data Monitoring Committee

None.

Page: 21 of 86

1.5 Schedule of Activities (SoA), Sampling and Assessments

Table 1-3: Schedule of Activities Lead-In Phase

STUDY			TREATMENT Period									
STUDY ELEMENT/PERIOD	Screening	Baseline										
VISIT acceptable time window (days)	(Up to 28 days before Week 1 Day 1)	(Up to 7 days before Week 1 Day 1)	2 [± 7 d]	4 [± 7 d]	8 [± 7 d]	12 [± 7 d]	16 [± 7 d]	24 [± 7 d]	36 [± 7 d]	52 [± 7 d]	EOT Visit 30 days (+7 days) after last dose) °	
PROCEDURE												
Informed consent	х											
General												
Demography		Х										
Inclusion and exclusion criteria	Х											
Relevant medical history (Includes substance use)		х										
PC history, classification (diagnosis, staging) including pre-treatments		х										
Prior/Concomitant medications ^d	Х				I		χ ^g	I	I	I		
CT/ MRI/ PSMA-PET bone scan ^a	Х											
Physical examination												
Full physical examination		х									х	
Safety												
AE /SAE/Discontinuations due to AE ^b						χ ^g					х	
ECOG performance status	Х	х		Х		Х		Х		Х		
Fasting glucose, fasting insulin, hemoglobin A1C, lipid profile, lean body mass ^f , fat mass ^f , weight		х		х		х		х	х	х	х	
Clinical chemistry (liver), hematology	X ^h	х		х		х		х	х	х	х	
DHT, DHEA, SHBG, androstenedione, prolactin, estradiol		х		x		x		х	х	х	х	
12-lead ECG ^j		Х		Х						Х	Х	
Vital signs	Х	Х		Х		Х		Х	Х	Х	Х	
Bone specific alkaline phosphatase (BSAP) and CTX		х		Х		х		×	Х	Х	х	

Clinical Study Protocol Global Amendment 1 BAY 1841788 / 21953

Page: 22 of 86

STUDY											
STUDY ELEMENT/PERIOD	Screening	Baseline				Treatment F	Period: Wee	ks			
VISIT acceptable time window (days)	(Up to 28 days before Week 1 Day 1)	(Up to 7 days before Week 1 Day 1)	2 [± 7 d]	4 [± 7 d]	8 [± 7 d]	12 [± 7 d]	16 [± 7 d]	24 [± 7 d]	36 [± 7 d]	52 [± 7 d]	EOT Visit 30 days (+7 days) after last dose) °
Efficacy											
Testosterone, free testosterone	х	Х	Х	Х	Х	Х	Х	Х	Х	Х	х
Serum PSA	Х	Х	Х	Х	х	х	Х	Х	х	Х	X
Gonadotropins, LH, FSH		Х	Х	Х	x	х	Х	Х	x	Х	x
24 DEXA scan		Х								Х	
Darolutamide dispensinge		Х		X X X		x					
Patient reported outcomes											
FACT-P		Х		Х		Х		Х	Х	Х	х
Surveys: physical function ⁱ		Х				х		Х		Х	

^a Radiological tumor assessments will be conducted only at screening to exclude presence of visceral metastases, and because these are not considered standard of care, will only be done at other times based on treating physician discretion and based on PSA progression. Investigators are encouraged to provide the results of PSMA-PET CT scans in the eCRF if performed (optional at baseline or during the study).

If patient treatment discontinued BEFORE completing the full 52-week treatment, please refer to the Active Follow Up Period SoA Table 1-5.

Bayer will provide questionnaires wherever validated version is available in the said language.

Abbreviations: A1C (hemoglobin) Glycated, AE adverse event, ALT Alanine aminotransferase, AST Aspartate aminotransferase, BSAP bone-specific alkaline phosphatase, CT computerized tomography, CTX C-terminal telopeptide, DEXA dual energy x-ray absorptiometry, DHEA dehydroepiandrosterone, DHT dihydrotestosterone, ECG Electrocardiogram, ECOG Eastern Cooperative Oncology Group, EOT end of treatment, FACT-P Functional Assessment of Cancer Therapy – Prostate Cancer, FSH-follicle-stimulating hormone, INR international normalized ratio, LH-luteinizing hormone, MRI magnetic resonance imaging, PC prostate cancer, PSA Prostate-specific antigen, PSMA-PET Prostate-specific membrane antigen positron emission tomography, PT prothrombin time, PTT partial thromboplastin time, SAE serious adverse event, SHBG sex hormone-binding globulin, SOC standard of care.

^b Safety assessments should be continued as per SOC at time of progression. After the 30-day short term follow-up period, only SAEs that are considered related to study intervention or study participation, with concomitant medications used to treat the event, should be reported by the investigator. Documentation of progression should be provided to the Sponsor (in CRF).

^c During the treatment period and up to 30 days following study intervention discontinuation, all (S)AEs are collected, regardless of causality.

^d For anti-cancer therapies, also collect prior to 28 days.

e Treatment compliance will also be assessed at each visit when study intervention is dispensed.

f Bioelectrical impedance scale to be used.

⁹ To be collected and updated as needed, not visit dependent. Eligibility assessments need to be completed prior to the patient being enrolled to the study.

^h Tests related to inclusion exclusion criteria should be performed at screening visit. Neutrophil count, Platelet count, Total bilirubin, ALT, AST, Creatinine, Creatinine, Creatinine clearance, PTT, PT, INR. All the other clinical chemistry and hematology are mentioned in Section 10.2, Table 10-1.

PROMIS, Self-Efficacy Assessment, and GODIN survey are not mandatory if translated version in not available. Questionnaires required are detailed in Section 10.4.

^j Assessment to be done in triplicate.

Page: 23 of 86

Table 1–4: Schedule of Activities Randomized Phase

STUDY			TREATMENT Period								
STUDY ELEMENT/PERIOD	Screening	Baseline		Treatment Period: Weeks							
VISIT acceptable time window (days)	(Up to 28 days before Week 1 Day 1)	(up to 7 days beforeW eek1 Day 1)	2 [± 7 d]	4 [± 7 d]	8 [± 7 d]	12 [± 7 d]	16 [± 7 d]	24 [± 7 d]	36 [± 7 d]	52 [± 7 d]	EOT 30 days (+7 days) after last dose ^c
PROCEDURE											
Informed consent	х										
General											
Demography		Х									
Inclusion and exclusion criteria	х										
Relevant medical history (Includes substance use)		х									
PC history, classification (diagnosis, staging) including pre-treatments		x									
Prior/Concomitant medications ^d	х						χ ^g				
CT/ MRI/ PSMA-PET bone scan ^a	х										
Randomization		Х									
Physical examination											
Full physical examination		Х									Х
Safety											
AE /SAE/ discontinuation due to AEs ^b						Xg					х
ECOG performance status	Х	Х		Х		Х		Х		Х	
Fasting glucose, fasting insulin, hemoglobin A1C, lipid profile, lean body massf, fat massf, weight		х		х		x		х	х	х	х
Clinical chemistry (liver), hematology	X ^h	х		х		х		х	х	х	х
DHT, DHEA, SHBG, androstenedione, prolactin, estradiol		х		x		х		х	х	х	х
12-lead ECG ^j		Х		Х						х	х
Vital signs	Х	Х	Х	х	Х	х		Х	Х	Х	Х

Page: 24 of 86

											1 450.
STUDY			TREATMENT Period								
STUDY ELEMENT/PERIOD	Screening	Baseline				Treatment	Period: Weeks	5			
VISIT acceptable time window (days)	(Up to 28 days before Week 1 Day 1)	(up to 7 days beforeW eek1 Day 1)	2 [± 7 d]	4 [± 7 d]	8 [± 7 d]	12 [± 7 d]	16 [± 7 d]	24 [± 7 d]	36 [± 7 d]	52 [± 7 d]	EOT 30 days (+7 days) after last dose ^c
Bone specific alkaline phosphatase (BSAP) and CTX		х		х		х		х	х		
Efficacy											
Testosterone, free testosterone	х	х	х	х	х	х	х	х	х	х	х
Serum PSA	х	х	Х	х	х	х	х	Х	х	х	Х
Gonadotropins, LH, FSH		х	Х	х	х	х	х	Х	х	х	Х
24 DEXA scan		х								х	
Study treatment dispensinge		х		х		х		х	х		
Patient reported outcomes											
FACT-P		Х		Х		х		Х	Х	х	Х
Surveys: physical function ⁱ		х				x		Х		x	

^a Radiological tumor assessments will be conducted only at screening to exclude presence of visceral metastases, and because these are not considered standard of care, will only be done at other times based on treating physician discretion and based on PSA progression. Investigators are encouraged to provide the results of PSMA-PET CT scans in the eCRF if performed (optional at baseline or during the study).

If patient treatment discontinued BEFORE completing the full 52-week treatment, please refer to the Active Follow Up Period SoA Table 1-5.

Bayer will provide questionnaires wherever validated version is available in the said language.

Abbreviations: A1C (hemoglobin) Glycated, AE adverse event, ALT Alanine aminotransferase, AST Aspartate aminotransferase, BSAP bone-specific alkaline phosphatase, CT computerized tomography, CTX C-telopeptide, DEXA dual energy x-ray absorptiometry, DHEA dehydroepiandrosterone, DHT dihydrotestosterone, ECG Electrocardiogram, ECOG Eastern Cooperative Oncology Group, EOT end of treatment, FACT-P Functional Assessment of Cancer Therapy – Prostate Cancer, FSH follicle-stimulating hormone, INR international normalized ratio, LH-luteinizing hormone, MRI magnet resonance imaging, PC prostate cancer, PSA Prostate-specific antigen, PSMA-PET Prostate-specific membrane antigen positron emission tomography, PT prothrombin time, PTT partial thromboplastin time, SAE serious adverse event, SHBG sex hormone-binding globulin, SOC standard of care.

^b Safety assessments should be continued as per SOC at time of progression. After the 30-day short term follow-up period, only SAEs that are considered related to study intervention or study participation, with concomitant medications used to treat the event, should be reported by the investigator. Documentation of progression should be provided to the Sponsor (in CRF).

^c During the treatment period and up to 30 days following study intervention discontinuation, all (S)AEs are collected, regardless of causality.

d For anti-cancer therapies, also collect prior to 28 days.

^e Treatment compliance will also be assessed at each visit when study intervention is dispensed.

f Bioelectrical impedance scale to be used.

⁹ To be collected and updated as needed, not visit dependent. Eligibility assessments need to be completed prior to the patient being enrolled to the study.

^h Tests related to inclusion exclusion criteria should be performed at screening visit. Neutrophil count, Platelet count, Total bilirubin, ALT, AST, Creatinine, Creatinine clearance, PTT, PT, INR. All the other clinical chemistry and hematology are mentioned in Section 10.2, Table 10-1.

¹ PROMIS, Self-Efficacy Assessment, and GODIN survey are not mandatory if translated version in not available. Questionnaires required are detailed in Section 10.4.

Assessment to be done in triplicate.

Page: 25 of 86

Table 1-5: Schedule of Activities Active Follow-up period

CTUDY ELEMENT/DEDIOD	Fau Dationto	ACTIVE FOLLOW UP PERIOD For Patients who discontinue treatment REFORE completing week 52 treatment for both Lead-in and Randomizer										
STUDY ELEMENT/PERIOD	For Patients who discontinue treatment BEFORE completing week 52 treatment for both Lead-in and Randomized Phases: Weeks											
VISIT (acceptable time window: days)	2 [± 7 d]	4 [± 7 d]	8 [± 7 d]	12 [± 7 d]	16 [± 7 d]	24 [± 7 d]	36 [± 7 d]	52 [± 7 d]				
Fasting glucose, fasting insulin, hemoglobin A1C, lipid profile, lean body mass ^a , fat mass ^a , weight		х		х		х	х	х				
Clinical chemistry (liver), hematology ^e		х		х		х	х	Х				
DHT, DHEA, SHBG, androstenedione, prolactin, estradiol		х		х		х	х	Х				
Vital signs		x		x		X	x	X				
Bone specific alkaline phosphatase (BSAP) and CTX		х		х		х	х	Х				
Efficacy												
Testosterone, free testosterone	Х	х	X	X	X	X	X	X				
Serum PSA	Х	х	X	x	x	X	x	X				
Gonadotropins, LH, FSH	х	х	Х	х	х	Х	х	Х				
24 DEXA scan								Х				
Patient reported outcomes												
FACT-P		х		х		Х	х	Х				
Surveys: physical function ^b				х		Х		Х				
Safety												
AE/SAE assessment ^c					Xd							

^a Bioelectrical impedance scale to be used.

Bayer will provide questionnaires wherever validated version is available in the said language.

Abbreviations: A1C (hemoglobin) Glycated, AE adverse event, ALT Alanine aminotransferase, AST Aspartate aminotransferase, BSAP bone-specific alkaline phosphatase, CT computerized tomography, CTX C-telopeptide, DEXA dual energy x-ray absorptiometry, DHEA dehydroepiandrosterone, DHT dihydrotestosterone, FACT-P Functional Assessment of Cancer Therapy – Prostate Cancer, FSH follicle-stimulating hormone, INR international normalized ratio, LH-luteinizing hormone, PSA Prostate-specific antigen, PT prothrombin time, PTT partial thromboplastin time, SAE serious adverse event, SHBG sex hormone-binding globulin.

^b PROMIS, Self-Efficacy Assessment, and GODIN survey are not mandatory if translated version in not available.

^c Concomitant medications used to treat related AEs that were unresolved at EOT will be capture in Active Follow-up period.

^d To be collected and updated as needed, not visit dependent.

e Tests related to inclusion exclusion criteria should be performed at screening visit. Neutrophil count, Platelet count, Total bilirubin, ALT, AST, Creatinine, Creatinine clearance, PTT, PT, INR. All the other clinical chemistry and hematology are mentioned in Section 10.2, Table 10-1.

Page: 26 of 86

2. Introduction

Darolutamide is a next-generation nonsteroidal androgen receptor inhibitor (ARI) for the treatment of prostate cancer, which binds with a high affinity and selectivity to the androgen receptor (AR) with potent and improved antagonism for AR.

Darolutamide has shown a very low blood-brain barrier penetration in rodents (Zurth et al. 2019) compared to enzalutamide and apalutamide. First data in humans also suggest that darolutamide has a favorable impact on brain blood flow compared to enzalutamide and that this might be attributable to difference in blood brain barrier penetration (BBB). Differences in BBB penetration of treatment and therefore, the effect on the central nervous system (CNS) may reduce the risk of CNS related side effects such as cognitive function, fatigue falls, dizziness, and depressed mood disorders.

Darolutamide plus androgen deprivation therapy (ADT) demonstrated significant improvement of metastasis-free survival (MFS) and overall survival (OS) in patients with non-metastatic castration resistant prostate cancer (nmCRPC) compared to ADT alone in the phase III ARAMIS study (Fizazi et al. 2019). The primary analysis in ARAMIS showed a median MFS improvement of 22 months (40.4 months in darolutamide compared with to 18.4 months in placebo arms HR of 0.41; 95% CI 0.34 to 0.50).

The final analysis showed a statistically significant benefit in overall survival (HR 0.69; 95% CI 0.53 to 0.88) and all other secondary end points such as time to pain progression, time to cytotoxic chemotherapy, and time to a symptomatic skeletal event.

Safety results of pivotal phase 3 study ARAMIS in nmCRPC showed ≤2% difference between the darolutamide and placebo groups for most AEs of interest, including CNS related AEs (i.e., falls, cognitive and mental impairment, depression), with fatigue as the only AE with a more that 10% incidence in the darolutamide arm (13.2% vs 8.3% in the placebo arm in the DB period).

